Date: 03/19/2015

Version Number: 01

Principal Investigator: [name]

Application Number: 2001935

Application Title: Combined effects of early behavioral intervention and propranolol on ASD

Protocol

1. Abstract

- a. Provide no more than a one page research abstract briefly stating the problem, the research hypothesis, and the importance of the research.

Finding effective treatments is a primary concern for individuals with autism and their families. Despite decades of research exploring treatment options, few treatments targeting core symptoms of the disorder, such as social communication, exist. Behavioral therapy involving intensive, individualized training is the mainstay of treatment for autism, but drugs targeting autism symptoms can be an important addition to treatment. Explorations of combined treatment approaches, in which drugs are used to augment the effects of behavioral therapy, are limited within the context of autism. Additionally, most currently available drugs target psychiatric symptoms associated with the disorder, including aggression, irritability, and obsessive behaviors, instead of core features.

Previous studies from our laboratory have examined the effects of the beta-blocker propranolol in adults and adolescents with autism. Propranolol inhibits the action of norepinephrine, a brain chemical that drives the stress response, or fight-or-flight, system. Heightened stress and anxiety in autism suggest propranolol as a potentially beneficial drug for this population. Our previous studies have demonstrated a benefit of single doses of propranolol for social functioning, as well as language-related cognitive abilities, in autism. We have also observed that participants with greater levels of stress reactivity demonstrate greater improvements in social functioning with propranolol, suggesting a potential method of predicting treatment response.

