In the proposed serial-dose, parallel design study, we plan to explore the effects of propranolol in combination with early intensive behavioral intervention in children with autism. Propranolol or placebo will be administered at the beginning of behavioral intervention sessions in a double-blinded, counterbalanced manner for the course of twelve weeks. Outcome measures will include assessments of social functioning, language, anxiety, adaptive behaviors, and other autism-related symptoms. This study will allow us to examine the effects of propranolol with multiple doses in a trial setting. In addition, this will be the first exploration of this drug's effects in children with autism, an important area of study given the benefits of early intervention. Previous studies involving pediatric migraine suggest that this drug can be used safely in young children. We will also determine whether measures of autonomic nervous system functioning and anxiety can predict which individuals will respond best to the drug. In this manner, we can begin to optimize and individualize combined treatment approaches for treating core symptoms of autism.

2. Objectives (include all primary and secondary objectives)

We propose to examine the effects of propranolol on social interaction in children with autism undergoing early intensive behavioral intervention (EIBI) in a 12-week, double-blinded, placebo-controlled pilot trial. We will also assess the effects of this combined therapeutic approach on language, anxiety, adaptive behaviors, and other autism-related behaviors in these individuals. Lastly, we will investigate how autonomic nervous system (ANS) activity, as measured by heart rate variability and pupillary light reflex, and baseline anxiety might predict the effects of propranolol on social functioning and our other outcome measures. We hypothesize that concomitant administration of propranolol will enhance the clinical benefit made through EIBI by improving social functioning, language, anxiety, adaptive behaviors, and other autism-related behaviors. We predict that this augmentation of EIBI's effects will only be apparent for the propranolol condition of the study. We also expect that ANS activity and anxiety levels will predict response to propranolol on our outcome measures.

3. Background (briefly describe pre-clinical and clinical data, current experience with procedures, drug or device, and any other relevant information to justify the research)

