Previous studies support the existence of altered noradrenergic activity in ASD, including early studies suggesting increased plasma (1) and urine (2) adrenergic metabolites in autism. Additionally, multiple studies indicate that ASD may be characterized by hyper-restrictive associative networks (3, 4) which may be related to increased noradrenergic signaling (5). These findings suggest the potential benefit of a pharmacological agent aimed at the noradrenergic system for this population. Propranolol, a centrally and peripherally active nonselective beta-adrenergic antagonist, reduces noradrenergic system activity. This anxiolytic has been used off-label for test anxiety (6) and performance anxiety (7) for several decades. Propranolol was first explored within the context of ASD in an uncontrolled case series, which reported improvements in language and sociability (8). Our laboratory has since investigated this agent's effects on a wide range of behaviors known to be affected in ASD, including verbal abilities (9, 10), working memory (11), and facial scanning (12) in single-dose psychopharmacological challenge studies in adults and adolescents with ASD. Most recently, we demonstrated a benefit of a single dose of propranolol on social functioning, assessed via conversational reciprocity, in a sample of 20 high-functioning adults and adolescents with ASD (13). This study also showed a potential association between resting autonomic activity, assessed via heart rate variability, and response to propranolol on the social task. These findings suggest a potential benefit of propranolol on core features of ASD and that treatment response may be predicted by certain markers. Accordingly, further study is necessary to examine if these potential benefits are not only maintained in serial doses, but also if these benefits extend to a younger population of individuals with autism. Behavioral therapy, including early intensive behavioral intervention (EIBI), has been shown to have lasting benefits for social functioning, language, and adaptive functioning in ASD. It has also been shown that behavioral intervention is more beneficial when introduced early in life; therefore, this critical early

stage following diagnosis would be also an opportune time to integrate pharmacological intervention with behavioral therapy to maximize therapeutic benefits.

4. Study Procedures

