- a. Study design, including the sequence and timing of study procedures (distinguish research procedures from those that are part of routine care).

The proposed study is a 12-week, parallel design, placebo-controlled pilot trial. For the purposes of this study, we will recruit 30 participants with ASD aged 3-8 who are currently enrolled in an EIBI program. ASD is defined in this study by the DSM-V criteria plus Autism Diagnostic Observation Schedule (ADOS) criteria for Autism. Participants will be screened for this formation as well as inclusion/exclusion criteria to determine their eligibility to participate in this study over the phone prior to obtaining written consent. A waiver of documentation of consent is requested for these screening purposes only. Written consent will be obtained prior to any other study-related procedures. The ADOS may be administered during the initial study visit if a prospective participant does not have ADOS scores from a previous assessment. Additionally, an intellectual assessment (IQ test), the Differential Ability Scales (DAS), may be administered at this time if previous scores do not exist.

Prior to participation in the study, informed consent will be obtained from both parents/legal guardians of the participant, and assent will be obtained from the participant. In addition, the parents and participants will be informed that they can terminate the procedure and exit the study at any time.

We will recruit participants during their participation in the EIBI program at the Thompson Center or other institutions in Missouri. The EIBI team provides one-on-one instruction for individuals with ASD, as they work toward treatment goals of learning new skills and minimizing challenging behavior. EIBI staff will be also be blinded to drug conditions. Given the highly individualized nature of EIBI, each participant's therapy will differ in frequency of sessions per week and length, as well as defined behavioral targets and the methods used to reach them. This variability will be accounted for via a stratified randomization approach (see below) as well as statistically during analyses after study completion.

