To determine the appropriate sample size for this study, we conducted a power analysis based on effect size estimates on our previous study examining the effects of propranolol on social functioning in ASD. The power analysis indicated that a sample size of 20 would achieve a proposed power of 0.80 at the significance level of $\alpha = .05$. Behavioral assessments will be compared across study time points and between drugs (propranolol and placebo) using repeated measures multivariate analyses of variance (MANOVAs). We will use simple linear regressions to determine whether variability in baseline autonomic nervous system functioning or anxiety serve as markers to predict treatment response. Interim data analysis will only be conducted for the purposes of presenting preliminary data at academic conferences. The investigational pharmacy will assist in unblinding collected data for these preliminary analyses, keeping investigators blinded throughout the study.

- d. Early stopping rules.

As this is a pilot trial exploring the effects of propranolol on social and language abilities, there are no behavioral endpoints that we could consider treatment success or failure prior to the completion of the study, thus we would not stop the study based on early evidence of treatment efficacy or futility. If safety becomes a concern due to side effects associated with propranolol, the PI (in consultation with the HS IRB) may decide

to stop the study early. However, this is not expected to occur given the minimal side effects known to be associated with this drug at these doses.

8. Risks

- a. Medical risks, listing all procedures, their major and minor risks and expected frequency.

The medical risks participants may encounter are those associated with taking the drugs used in this study. Below are the descriptions and side effects associated with each drug:

Propranolol [pro-pran'-o-lol] is commonly used to decrease high blood pressure. This drug can cause problems for persons with depression, diabetes, thyroid disease, very slow heart rates, very low blood pressure, fluid in the lungs from heart failure, and asthma. The side effects related to this drug are given below. These symptoms are most present within 5 hours of the drug administration. None of these symptoms will be present once the single dose is washed out of the system, which can take up to 24 hours.

- Very Likely: Decreased Blood Pressure and/or Slow Heart Rate

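### Does sizing a 12-week trial in young children from a single-dose effect in adults and adolescents undermine the 0.80 power stated in Section 7c?

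*Combined protocol and SAP*

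**What the plan says.** Section 7c says the sample size was determined "based on effect size estimates on our previous study examining the effects of propranolol on social functioning in ASD", and continues: "The power analysis indicated that a sample size of 20 would achieve a proposed power of 0.80 at the significance level" of .05. It does not give the effect size, its standard deviation, the test or the sidedness, and it does not say whether 20 is a total or a per-arm figure.

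The source is not cited by number, but the rest of the protocol narrows it down:

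- Section 1 (Abstract): "Previous studies from our laboratory have examined the effects of the beta-blocker propranolol in adults and adolescents with autism". It adds: "Our previous studies have demonstrated a benefit of single doses of propranolol for social functioning".
- Section 1 also says of this trial that "this will be the first exploration of this drug's effects in children with autism", so the source cannot have been paediatric.
- Section 3 (Background) describes the laboratory's studies of verbal ability, working memory and facial scanning as done "in single-dose psychopharmacological challenge studies in adults and adolescents with ASD". It then describes one social-functioning study: a single dose in 20 high-functioning adults and adolescents, scored on conversational reciprocity.
- Section 3 concludes that carry-over still needs study: "examine if these potential benefits are not only maintained in serial doses, but also if these benefits extend to a younger population of individuals".

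Section 4a sets the recruitment target: "we will recruit 30 participants with ASD aged 3-8 who are currently enrolled in an EIBI program". Allocation is half to each arm and follow-up is 12 weeks. No section explains the step from 20 to 30.

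**The concern.** The planning effect seems to come from a setting that differs from this trial in age, regimen and outcome. The source used one dose in high-functioning adults and adolescents and scored conversational reciprocity. This trial uses repeated doses over 12 weeks in children receiving individualised behavioural therapy, with the GSOM and SRS as primary outcomes. Section 3 treats carry-over as an open question, yet Section 7c applies the effect without a discount.

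A reader who sees 30 recruited against 20 required may conclude that the trial is comfortably powered. If the effect in children is smaller, actual power could be far below 0.80, and a non-significant result could be misread as showing that propranolol adds nothing to behavioural therapy.

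**Working it through.** **The stated figure.** N = 20 can be neither reproduced nor refuted, because Section 7c gives no effect size, test or sidedness. It can only be solved backwards.

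**Inputs.** From Section 7c: N = 20, power 0.80, alpha .05. From Section 4a: 30 recruited, half per arm, so 15 per arm. Assumptions not in the documents: a two-sided test, 20 as the total (10 per arm), a two-group comparison of change from baseline, and the carry-over shares.

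**Formula.** With n per arm and standardised difference d (in SDs of change), power is the upper tail of a noncentral F with 1 and 2n - 2 degrees of freedom and noncentrality n d²/2, beyond the 5% critical value.

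**Step 1: implied effect.** Power 0.80 at n = 10 gives d = 1.325.

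**Step 2: effect needed with 30 children.** Power 0.80 at n = 15 gives d = 1.060. The share required is 1.060/1.325 = 0.80. The normal approximation gives √(20/30) = 0.816. The 80% is therefore little more than the ratio of the two sample sizes. It would arise in any trial that recruits 30 against a calculated 20, and says nothing specific about propranolol.

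**Step 3: power with 15 per arm, by share of d = 1.325 carried over.**

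| Share | d | Power |
|---|---|---|
| 100% | 1.325 | 0.94 |
| 90% | 1.192 | 0.88 |
| 80% | 1.060 | 0.80 |
| 75% | 0.994 | 0.75 |
| two-thirds | 0.883 | 0.65 |
| one half | 0.662 | 0.42 |

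A 2-df drug-by-time test over three visits, in univariate or multivariate form, gives nearly the same required share (0.804 and 0.789). This is weak corroboration, because each test is solved back from the same assumed N = 20.

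**Step 4: sensitivity to the reading of 20.**

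- 24 completers (12 per arm): d = 1.197 is needed, and 1.197/1.325 = 0.90 of the effect.
- 20 meant per arm: the implied d is 0.909. With 15 per arm the share needed is 1.060/0.909 = 1.17, and full carry-over gives power 0.67.
- 20 from a paired calculation: the implied paired effect is 0.660. Converting by d = 0.660 × √(2(1 - ρ)) and assuming ρ of 0, 0.5 and 0.7 gives d = 0.934, 0.660 and 0.512. Power with 15 per arm is then 0.69, 0.42 and 0.27 at full carry-over.

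**Step 5: precision.** The 95% interval half-width for a difference in change at 15 per arm is t(0.975, 28) × √(2/15) = 2.048 × 0.365 = 0.748 SD.

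**Step 6: cost of resizing, with 20 as the total.** Power 0.80 needs 44 children at two-thirds carry-over and 74 at one half. That is 44 - 30 = 14 or 74 - 30 = 44 more than planned.

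**The passages side by side.** Section 3 says that benefit in serial doses and at younger ages has to be studied. Section 7c uses an existing estimate to size that study. Section 3 does not say the effect holds in children, and Section 7c does not say it has been established there. Both statements can stand together.

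**The case for a change.** The strongest case for a change runs as follows. Section 7c does more than call the study a pilot: it claims 0.80 power as the basis for the sample size, and Section 2 states a directional hypothesis. The pilot label does not support that number. Reading 20 as the total is the lenient choice, since the per-arm reading, a paired source calculation and drop-out all raise the share of the effect needed. The extra 10 children cannot serve in full both as a drop-out allowance and as a margin for a smaller effect. A few added sentences would cost nothing.

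Much of this stands. The source effect is very probably from single-dose work in adults and adolescents, no discount is stated, and power falls quickly if carry-over is poor. The change of outcome from conversational reciprocity to the GSOM and SRS adds to the doubt. Section 7c would be more informative with the effect size, its source, the test and the meaning of 20.

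It does not establish an error. On the reading that the wording favours, the design exceeds its claimed power under its own assumption. The less favourable readings show that the description is incomplete, not which calculation was done. The feared misreading is not in the plan either: Section 7a describes the primary aim as exploration, Section 4f names no behavioural endpoint that would count as treatment failure, and nothing says a null result would be taken as no effect. An interval of about ±0.75 SD is what a trial of this size gives, and the documents define no useful effect against which to call it inadequate.

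**Conclusion.** No change to the plan follows. The gap is real, but it is one of reporting. An effect estimate borrowed from the closest earlier work is a usual and defensible start for a first study in children, and no paediatric data existed from which to derive a discount. How much to discount is a matter on which statisticians would differ. Any particular choice, such as 44 or 74 children, would rest on an assumed share and would enlarge a first exploratory study. Keeping 30 is a fair trade-off.

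Writing an 80% condition into Section 7c would not improve it, because the correct percentage depends on facts only the sponsor holds: about 80% if 20 is the total and all 30 children complete, about 90% with 24 completers, and about 117% if 20 is per arm. Analysts of a pilot this size can be expected to report the between-arm differences with confidence intervals and to interpret a null result cautiously without a rule that says so.

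The conclusion rests on reading 20 as the total for a two-arm, two-sided comparison. If the sponsor's calculation was per arm, 30 children would fall short of the stated power even at full carry-over (0.67). That would be a different and more serious point, but the documents do not show it.

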Upon study enrollment, participants will be randomized to receive either placebo or propranolol for a period of 12 weeks during the study. Drug randomization will be counterbalanced to ensure that half of the participants will receive placebo and the other half will receive propranolol. Randomization will also be double-blinded so that neither participants nor the researchers performing analysis will be aware of the identity of the drug being administered. As participants will be receiving varying levels of intensity of EIBI (number of hours per week), randomization will also be stratified according to different levels of intensity to ensure approximately equal distribution of EIBI intensity between the two drug groups.

The following are brief descriptions of the drugs to be administered:

Propranolol [pro-pran'-o-lol] blocks the brain's and body's use of norepinephrine both centrally and peripherally and also is commonly used to decrease high blood pressure.

Placebo [pla-see'-bo] is a physiologically inactive suspension that looks like other drugs.

Drug administration: Propranolol will be administered in the form of a liquid dose via oral syringe by the participants' parent/caregiver an hour before each EIBI session. Drug administration will begin after the first (baseline) study visit. To minimize risk, the bodyweight adjusted minimum dose of propranolol used safely for test anxiety in healthy adults (10mg) will be used (see table below):

Bodyweight (kg)	Dose (mg)
> 30	4
22.5 - 30	3
15 - 22.5	2
< 15	N/A

This more cautious dosing strategy will be utilized for safety purposes, as children may be less able to report potential side effects. Participants weighing less than 15kg will be excluded for safety reasons.

Heart rate and blood pressure monitoring: Participants with a heart rate of less than 60 or a systolic blood pressure of less than 75 at the outset of the study will be excluded. Heart rate and blood pressure will also be measured via wrist cuff at each study visit. If on any measurement the heart rate or systolic blood pressure is abnormal, the PI will be immediately notified. At this point, the PI may withdraw the participant from the study for safety reasons.

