During the study, participants will undergo ANS activity and behavioral assessments (discussed below) at three separate study visits at the following time points: (1) prior to drug administration, for establishment of a baseline (week 0); (2) at approximately week 6; and (3) at the end of week 12. Each study visit is expected to last approximately an hour and half.

ANS Measurements: At each study visit, ANS measurements will be performed to assess autonomic activity. Heart rate variability (HRV), measured via electrocardiogram, will be used to assess sympathetic and parasympathetic nervous system activity. Electrodes will be placed on the chest region in the typical manner, and signal from the electrodes will be amplified by an ECG 100C module connected to a BIOPAC MP150 data acquisition system. Measurements will be recorded for a period of 8 minutes, allowing for 3 minutes of acclimation to the equipment.

We will also evaluate ANS activity via the pupillary light reflex (PLR), a simple functional neurological test measuring pupil constriction and recovery in response to stimulation via a short light flash. During the test, the participant will sit comfortably in a

chair or will be seated on a parent's lap about 1 m from the PLR system. A red-filtered movie will be shown on a projector screen behind the PLR system to attract the participant's attention. During the test, participants' PLR will be assessed in both light- and dark-adapted conditions. A total of 10 trials, each lasting 2.5 sec followed by a 25-30 sec interval, will be performed for each stimulation condition.

Behavioral Assessments: Behavioral tasks and questionnaires will also be performed at each study session. The following assessments will be completed by the participant with ASD:

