Participation in this study will last 12 weeks and will involve 3 visits to the Thompson Center for Autism & Neurodevelopmental Disorders lasting approximately an hour and a half each. If a private room is not available at the Thompson Center when a participant's visit needs to be scheduled, the visit will take place at the Center for Translational Neuroscience (M741) in the Medical Sciences Building instead.

c. Blinding, including justification for blinding or not blinding the trial, if applicable.

This study will be double-blinded for the purposes of removing any bias that could be introduced if either the researchers or the study participants are aware of which drug they are taking at a given time. Blinding of the drugs will be conducted by the University Hospital's Investigational Pharmacy. In the case of emergency, the PI and research staff running study sessions will have access to unblinding information in the form of a sealed envelope.

d. Justification of why participants will not receive routine care or will have current therapy stopped.

Routine care for this population will not be affected by this study. Participants will be able to continue routine care, including behavioral therapy or other medications. Potential participants taking medications that are exclusionary for this study will not be enrolled.

e. Justification for inclusion of a placebo or non-treatment group.

A placebo arm of this study will allow for statistical comparisons between behavioral performance for participants who are taking placebo versus propranolol. The parallel design of the trial will involve half of the participants receiving propranolol and the other half receiving placebo. Drug randomization will be counterbalanced.

f. Definition of treatment failure or participant removal criteria.

As this is a pilot trial exploring the effects of propranolol on social and language abilities, there are no behavioral endpoints that we would consider treatment failure. However, for the safety of the participants, if at any measurement taken, a participant's heart rate or blood pressure is abnormal or if the participant is experiencing an adverse reaction to the drug the PI will be immediately notified. At that point, if the PI determines it is necessary, the participant will be instructed to discontinue taking the drug and will be removed from the study.

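### Section 7c appears to treat the pre-drug week-0 score as a response and has no EIBI-intensity term; using both as covariates, with a named primary test, is more efficient at little cost

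*Combined protocol and SAP*

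**What the plan says.** Section 7c: "Behavioral assessments will be compared across study time points and between drugs (propranolol and placebo) using repeated measures multivariate analyses of variance (MANOVAs"). It names no effect, visit or covariate as primary. Section 7a names two primary measures, the GSOM and the SRS, without a time point.

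Section 4a places the first visit "prior to drug administration, for establishment of a baseline (week 0") and the others "at approximately week 6; and (3) at the end of week 12". Behavioural measures are taken at all three.

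On EIBI, section 4a says of differences between children's programmes: "This variability will be accounted for via a stratified randomization approach (see below) as well as statistically during analyses after study completion". It adds that "randomization will also be stratified according to different levels of intensity". The number of levels is not given, and section 7c contains no EIBI term.

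The planned size is given in section 4a: "we will recruit 30 participants with ASD aged 3-8 who are currently enrolled in an EIBI program", with half on each drug. The hypothesis in section 2 is that the augmentation of EIBI's "effects will only be apparent for the propranolol condition of the study".

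**The concern.** Three tests fit the sentence in section 7c: a drug main effect over all visits, a drug-by-time interaction, or a comparison at one visit. They differ widely in power, and the plan does not choose. The section 2 hypothesis points to drug by time. That test is valid, but it in effect subtracts the whole baseline score, where a regression on baseline would remove more noise. The main effect averages in a visit at which no drug effect can exist.

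The EIBI gap is a commitment not carried through: the factor used to stratify, and promised in the analysis, is absent from the statistical plan.

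At 15 per arm, the use made of data already collected affects the chance of seeing a real effect. Section 7c also allows unblinded preliminary analyses for conferences, so the primary test is best fixed before by-arm results exist.

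**Working it through.** **The plan's own figure.** Section 7c states that 20 participants give power 0.80 at alpha .05. No effect size, SD, test or sidedness is given, so this cannot be reproduced. Solved backwards (two-sided t-test), it would need a standardised difference of 1.33 with 10 per arm, or 0.66 for 20 paired differences. Neither can be checked against the documents.

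**Inputs.** From the documents: 30 children, 1:1 (n = 15 per arm), visits at weeks 0, 6 and 12, alpha 0.05. Assumed: two-sided test, one outcome, unit SD, complete data, two balanced strata that predict nothing, equal correlation r between visits, and effects (d6, d12) at weeks 6 and 12.

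**Noncentrality λ of each test**, with n/2 = 7.5:

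- Main effect over three visits: λ = 7.5 × [(0 + d6 + d12)/3]² ÷ [(1 + 2r)/3]; F(1, 28).
- Drug by time (two change scores): λ = 7.5 × (2·d6² − 2·d6·d12 + 2·d12²) ÷ [3(1 − r)]; F(2, 27).
- Joint test of weeks 6 and 12, adjusted for baseline and stratum: λ = 7.5 × d′V⁻¹d, where d = (d6, d12) and V has diagonal 1 − r² and off-diagonal r − r². Multiply by 26/27 for estimating the baseline slope; F(2, 25).
- Week-12 ANCOVA: λ = 7.5 × d12² ÷ (1 − r²), times 26/27; F(1, 26).

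**Worked case, r = 0.5, effects 0.5 then 1 SD.**

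- Main effect: 7.5 × 0.25 ÷ 0.667 = 2.81, power 0.37.
- Drug by time: 7.5 × 1.5 ÷ 1.5 = 7.50, power 0.635.
- Adjusted joint test: 7.5 × 1.375 × 26/27 = 9.93, power 0.76.
- Week-12 ANCOVA: 7.5 ÷ 0.75 × 26/27 = 9.63, power 0.85.

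**Range.** Simulated power (20,000 trials per setting), which the formulas match to within about 0.006:

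| Effects (wk 6, wk 12) | r | Main effect | Drug × time | Adjusted 2-df | Week-12 ANCOVA |
|---|---|---|---|---|---|
| 0.5, 1 | 0.5 | 0.371 | 0.633 | 0.760 | 0.845 |
| 0.5, 1 | 0.7 | 0.321 | 0.856 | 0.898 | 0.950 |
| 1, 1 | 0.5 | 0.583 | 0.769 | 0.901 | 0.845 |
| 1, 1 | 0.7 | 0.507 | 0.943 | 0.971 | 0.950 |
| 1, 0.5 | 0.5 | – | 0.634 | 0.758 | 0.320 |
| 1, 0.5 | 0.7 | – | 0.857 | 0.898 | 0.437 |

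The gain of the adjusted 2-df test over drug by time runs from 0.971 − 0.943 = 2.8 points to 0.901 − 0.769 = 13.2 points. Because the stratum predicts nothing here, all of it comes from baseline. Over 40 settings (growing, sustained and fading effects; equal or AR(1) correlation of 0.5 to 0.8), this test was ahead in 39 and level in one (0.980 against 0.981; AR(1) 0.8, fading effect).

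The week-12 contrast is not uniformly better. It roughly halves power if the effect fades (0.32 against 0.63 at r = 0.5). It also trails drug by time for a sustained effect under AR(1) 0.8 (0.92 against about 0.96).

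**The stratum.** Suppose EIBI intensity explains 20% of the variance left after baseline, at the post-baseline visits only. Omitting it then lowers the type I error to 3.2–3.6%, and including it adds 1.6 to 5.2 points to the 2-df test. If EIBI shifts all visits alike, drug by time and week-12 ANCOVA keep 4.6–4.9% error without it, and nothing is gained.

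**Cost.** If baseline predicts nothing (r = 0, 1 SD), an unadjusted t-test at week 12 has power 0.753 and the adjusted one 0.731, a loss of 2.2 points. Adding a useless two-level stratum to the 2-df test costs 0.721 − 0.715 = 0.6 points.

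**Missing data.** At an assumed 10% loss per interval, 30 × 0.9 × 0.9 = 24.3 children are complete. The week-12 contrast from a likelihood-based repeated-measures model then has power 0.742 (r = 0.5) and 0.888 (r = 0.7) for 1 SD at week 12. Complete-case week-12 ANCOVA gives about 0.74 and 0.88. The model adds essentially no power.

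**The case against.** This is an exploratory pilot. Week 0 as a response is not wrong in itself: drug by time is valid, and so is a longitudinal model with a common baseline mean. Section 2 points to drug by time, so the main-effect powers are a weak comparator. EIBI is already handled in the randomisation and promised in the analysis, and omitting the stratum is at worst conservative. Much of this stands. The fair comparison is with drug by time, where the gain is modest. The unnamed test is mainly missing detail, and the EIBI point is a failure to carry section 4a's promise into section 7c. Pilot status does not dispose of the matter, because section 7c claims 0.80 power at alpha .05 and so intends hypothesis tests.

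A reader might infer more than the documents support:

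- *That a week-12 ANCOVA is always the better test.* It is not if the effect fades, and the documents give no time course.
- *That a mixed model recovers power lost to dropout.* At the loss assumed above it does not. Section 4f says that, where the investigator judges it necessary, "the participant will be instructed to discontinue taking the drug and will be removed from the study", but it gives no rate. The 10% is an assumption, and the simulation did not let loss differ by arm.
- *That the investigators will choose the contrast after seeing results.* Section 7c keeps them blinded. The most that can be said is that presented by-arm results could inform a choice left open.

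Two limits remain. All powers are for one outcome at 0.05, while two measures are primary; testing each at 0.05 with no error rule allows a familywise rate of up to 0.10. That is a separate matter, which this change does not settle.

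**Conclusion.** The point holds as one of efficiency and specification, not validity. On its natural reading, which section 7c does not state outright, the plan spends the pre-drug score as a response and omits the stratification factor that section 4a undertook to account for. Adjusting for both and testing weeks 6 and 12 jointly gains about 3 to 13 points over drug by time, on assumed effects of 1 SD at the larger visit, equal correlation of 0.5 to 0.7, 15 per arm and complete data. The gain shrinks to a near tie at AR(1) 0.8. The stratum contributes only if EIBI intensity predicts outcome beyond baseline. No power gain is claimed for the handling of missing data. The change should be made; the trial is not unsound without it.

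**What to change.** In section 7c, for the GSOM and the SRS:

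- Take weeks 6 and 12 as responses, with week 0 and the EIBI-intensity stratum as covariates. Arm, baseline and stratum are each crossed with visit, with unstructured covariance and small-sample degrees of freedom.
- Name the primary test before the first unblinded preliminary analysis. The joint 2-df arm test over both visits kept or tied its advantage in every time course tried. Name the week-12 difference instead only if the effect is expected to persist or grow to week 12.
- Report the arm difference at each visit with a 95% CI.
- State the number of EIBI strata and keep it small.

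A likelihood-based fit that keeps children with one post-baseline score is reasonable, but should not be justified by power.

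Cost: protocol wording and a few degrees of freedom (one for baseline, one fewer than the number of strata). With two strata that is about 2 points of power or less, even if baseline predicts nothing. No extra enrolment is needed.

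Continuing assessments after a child stops drug is optional and is not part of this low-cost change. It would alter the removal clause in section 4f and add payments of $25 per visit, plus $75 travel where eligible (section 10).
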